#### Traumatic stress and cue response task

The Cue and Stress Response Task will be performed at the 4- week time-point using methodology developed in [name]'s lab, similar to those in used in past studies with alcohol dependent patients [84]. [name] will provide consultation on the implementation of these methods. Briefly, imagery scripts will be developed at baseline. Traumatic stress imagery scripts will be based on a recent highly stressful traumatic situation the participant has experienced unrelated to alcohol use. Alcohol cue scripts will be derived from a recent event that included alcohol-related stimuli and led to alcohol use. Neutral or relaxing scripts will also be developed. All scripts will be developed by obtaining specific details of stimulus and response, including contextual details, cognitive and verbal content, affective experience, and bodily sensations. These details form the basis of a 5-minute imagery script, which will be developed for each of the three conditions. Imagery sessions will be structured with a 5-minute pre-imagery period, a 5-minute imagery period, and a 5-minute recovery period. Pulse, skin conductance, heart rate variability, and blood pressure will be monitored during each imagery session with an ADInstruments PowerLab 4/30 Galvanic Skin Response device and a Contec Patient Monitor. In Human laboratory studies with CBD, skin conductance and amygdala activation were reduced by CBD in a closely correlated manner [52], suggesting threat-related sympathetic arousal may serve as a proxy for amygdala activation [53].

Participants will complete Likert scale ratings of vividness, craving, anxiety, and the 30-item Differential Emotion Scale [84] following each of the three periods. After each condition, a progressive relaxation procedure will be implemented to facilitate return to baseline of vital signs, craving and anxiety, an approximate period of 10 minutes, as shown in previous research from the [name] lab [84]. The entire imagery protocol will take 120 minutes. The order of the sessions will be randomized and counterbalanced among participants. The task will be completed at T6 (the end of 4 weeks of treatment with 600mg daily). At this point, we expect steady-state plasma CBD levels to have been reached.

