#### #S17-00949

will be monitored during each imagery session with an ADInstruments PowerLab 4/30 Galvanic Skin Response device and a Contec Patient Monitor. In Human laboratory studies with CBD, skin conductance and amygdala activation were reduced by CBD in a closely correlated manner [52], suggesting threat-related sympathetic arousal may serve as a proxy for amygdala activation [53]. Participants will complete Likert scale ratings of vividness, craving, anxiety, and the 30-item Differential Emotion Scale [84] following each of the three periods. After each condition, a progressive relaxation procedure will be implemented to facilitate return to baseline of vital signs, craving and anxiety, an approximate period of 10 minutes, as shown in previous research from the [name] lab [97]. The entire imagery protocol will take 120 minutes. The order of the sessions will be randomized and counterbalanced among participants. The task will be administered at T6, following 4 weeks of treatment with CBD or placebo. At this point, we expect steady- state plasma CBD levels to have been reached.

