### 20.3 Description of Statistical Methods

### 20.3.1 General Approach

We recognize that the relatively small sample sizes proposed in the RCT are not likely to produce statistical significance, unless the effect sizes are remarkably high. We will carry out a full Mixed Model Repeated Measures (MMRM) statistical analysis in case CBD does perform so well. However, the main focus of the statistical analysis of the results of the trial will be to characterize the effect sizes and response rates across the various measurement domains and the profiles of individuals who are treatment successes. The intent to treat (ITT) population will contain all randomized patients who receive at least one dose of double-blind study medication and from whom at least one post-baseline (B1) efficacy measurement is obtained while on study medication. The efficacy analysis will be based on the ITT population. Two-sided hypothesis testing will be utilized. Tests with p-values less than or equal to 0.05 will be considered statistically significant, while those less than equal to 0.10 will be considered suggestive. Since this trial is the first use of this treatment for this diagnostic indication, no adjustments of p-values for multiple comparisons will be made. Thus, all control of type 1 error is contrast-wise. All confidence intervals will be two-sided with 95% confidence. Mean treatment effect, standard errors, and 95% confidence intervals will be derived from fully adjusted models on outcomes averaged across the treatment period. Cohen's d and p-values will be calculated from fully adjusted models with appropriately transformed outcome variables. For dichotomous drinking outcomes, prevalence rates will be calculated. Odds ratios (ORs) and p-values will be derived from logistic regression models including treatment group.

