### 20.3.3 Analysis of the Secondary Endpoint(s)

For hypothesis 3a: Mechanism, traumatic stress-induced craving: The primary outcome measure will be alcohol craving. Alcohol craving outcomes within a session will be examined in terms of a created measure of a difference of difference scores: first, the difference score of the alcohol craving response to trauma and to neutral challenges calculated for the Pre and for the Post session time points, and second, the difference of the

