#### #S17-00949

scores between Post and Pre. This difference measure of alcohol craving will be calculated at Baseline, and at week 6 of the clinical trial (T8). The outcome analysis will be conducted with an MMRM model that includes fixed effects for treatment C, (CBD vs. placebo) and clinical trial time T, a random effect for subjects, and a treatment by clinical trial time interaction (C\*T). The model will provide least-square mean estimates of difference scores at each session for each treatment. Between treatment outcome contrasts will be performed at Baseline, as a measure of the equivalence of the groups, and at T6 and for the difference between T6 and Baseline. For parameter estimation, the form of the covariance matrix will follow the procedures described for the analysis of Aim 1. Secondary outcome measures will be Negative Emotion, and Psychophysiological arousal. These outcomes will be analyzed in a similar manner to the primary outcome, alcohol craving.

For Hypothesis 3b: Mechanism, AUD and PTSD related measures and cognition (craving, self-efficacy, anxiety, cognitive measures) will be analyzed in the same way as the primary outcome for alcohol use. The primary contrast is change from baseline (B1) at week 6 (T8).

For Hypothesis 3c: Mechanism, anandamide, within- and between-group comparisons of plasma anandamide levels will be assessed following 45 minutes (T1), 1 day (T2), 1 week (T3), 2 weeks (T4), 4 weeks (T6), 6 weeks (T8) of treatment with CBD vs. placebo, and one week (T9) after the completion of treatment. Effects of dose will be assessed and the interaction between group and time- point will be evaluated.

For Hypothesis 4, plasma CBD and THC levels will be analyzed in the same manner as anandamide in Hypothesis 3c.

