### 20.5 Measures to Minimize Bias

### 20.5.1 Enrollment/Randomization/Masking Procedures

Enrolled participants that pass screening will be randomized using a 5:3 ratio to receive either 600mg CBD/day (PO) or placebo respectively for 6 weeks (N=30 participants on CBD and N=18 participants on placebo). Treatment assignment will be known only to a designated unblinded study staff member in charge of dispensing study medication under direct PI supervision, but the blind can be broken if necessary, e.g., in case of a serious reaction during drug administration.

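### The Hypothesis 3a trauma-craving model leaves out the randomised imagery order; if order shifts the score this costs precision, but it does not bias the CBD v placebo comparison

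*Combined protocol and SAP*

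**What the plan says.** **Task (protocol section 4.2.2, Traumatic stress and cue response task, and section 7.1.8).** Five-minute scripts are used, "which will be developed for each of the three conditions": trauma, alcohol cue, and neutral or relaxing. "Imagery sessions will be structured with a 5-minute pre-imagery period, a 5-minute imagery period, and a 5-minute recovery period". On order: "The order of the sessions will be randomized and counterbalanced among participants". On washout: "After each condition, a progressive relaxation procedure will be implemented to facilitate return to baseline of vital signs, craving and anxiety", for about 10 minutes. The whole protocol takes 120 minutes.

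**Outcome (section 20.3.3, Hypothesis 3a).** Craving is analysed as "a created measure of a difference of difference scores": trauma minus neutral at Pre and at Post, then Post minus Pre.

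**Model (section 20.3.3).** It "includes fixed effects for treatment C, (CBD vs. placebo) and clinical trial time T, a random effect for subjects", together with the treatment-by-time interaction. Negative emotion and psychophysiological arousal are analysed in a similar way. No order, sequence or period term appears here or elsewhere. Section 20.3.1 refers to fully adjusted models but lists no covariates, and section 20.1 leaves a formal SAP to be written before database lock and unblinding.

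**Size and test level.** Section 20.5.1 gives "N=30 participants on CBD and N=18 participants on placebo". Section 20.3.1 sets two-sided tests: "Tests with p-values less than or equal to 0.05 will be considered statistically significant".

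**The concern.** Order is a factor that the trial itself randomises, and the relaxation step shows that the authors considered carry-over between scripts. If hearing trauma before neutral moves the score, a model without order leaves that movement in the residual. Counterbalancing is stated across participants, not within arm, so the two arms can differ by chance in the share who heard trauma first.

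What is at stake is precision. Section 20.3.1 says that the trial's main purpose is to characterise effect sizes, and Hypothesis 3a is its test of the proposed mechanism in at most 48 people.

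**Working it through.** **1. What survives the double difference.** Let T and N be the craving ratings for trauma and neutral, and read Pre and Post as before and after imagery (the plan does not define them further). The score is

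S = (T_post − N_post) − (T_pre − N_pre) = (T_post − T_pre) − (N_post − N_pre).

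If neutral follows trauma with leftover craving c_pre at Pre and c_post at Post, S shifts by c_pre − c_post. The shift is zero if the leftover is constant and positive if it is fading. Sensitisation or habituation would also shift S.

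**2. Chance imbalance between arms.** Trauma comes before neutral in three of the six possible orders, so assume 24 of 48 participants in each class, with order drawn without regard to arm. The number k of CBD participants who hear trauma first is then hypergeometric (48, 24, 30).

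- Var(k) = 30 × 0.5 × 0.5 × 18/47 = 2.872, so SD(k) = 1.695.
- Arm difference in share = k/30 − (24 − k)/18, which changes by 1/30 + 1/18 = 0.0889 per person. Its SD is 1.695 × 0.0889 = 0.151.
- P(difference of 0.20 or more, either direction) = 0.135. P(0.30 or more) = 0.036.

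**3. Variance inflation.** The documents give no order-effect size, so a range is assumed. A 50:50 factor that shifts the score by o residual SD adds o²/4 to the variance. Without order, the standard error of the arm difference is √(1/30 + 1/18) = 0.298 residual SD.

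| Assumed o | Variance factor 1 + o²/4 | SE factor | SD of chance shift, 0.151 × o |
|---|---|---|---|
| 0.3 | 1.02 | 1.01 | 0.045 |
| 0.5 | 1.06 | 1.03 | 0.075 |
| 1.0 | 1.25 | 1.12 | 0.151 |

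The last column is not a further cost: (0.075/0.298)² = 0.06 and (0.151/0.298)² = 0.26, which is the same inflation to within rounding and the factor 48/47.

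**4. Reference effect for power.** Section 20.4 states an effect size of 0.939 for 0.8 power. By the noncentral t, two-sided 0.05, that figure reproduces at 25 v 15 (d = 0.9389), not at 30 v 18, where the effect for 0.80 power is d = 0.853. The power comparison below uses 0.853. The mismatch does not affect this point.

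**5. Power with and without the term.** The calculated column is the noncentral-t power at 0.853/√(1 + o²/4). The simulation used 20,000 trials per setting with one score per participant, residual SD 1, order 24/24 and a true effect of about 0.85. Its Monte Carlo error is about √(0.8 × 0.2/20,000) = 0.003.

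| Assumed o | Calculated, no term | Simulated, no term | Simulated, with term |
|---|---|---|---|
| 0 | 0.800 | 0.800 | 0.793 |
| 0.3 | 0.791 | 0.789 | 0.790 |
| 0.5 | 0.776 | 0.773 | 0.787 |
| 1.0 | 0.707 | 0.706 | 0.789 |

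Without the term, the mean estimate was 0.852 to 0.853 and the type I error was 0.047 to 0.052. This is a two-group linear model of a single score, not the full repeated-measures model.

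**The case against.** The strongest case against is that the design already deals with most carry-over. The relaxation period is meant to return craving and anxiety to baseline, and the protocol cites earlier work for that. The second difference removes any leftover level that is the same at Pre and Post. If the task were run at baseline and again on treatment in the same order, a stable order effect would also cancel in the change from baseline. The analysis is secondary, section 20.3.1 concedes that significance is unlikely, and a formal SAP is still to come.

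Much of this stands, and it is why the point is an efficiency refinement. It does not remove the point. Relaxation limits carry-over without ensuring that none is left, and fading carry-over survives the double difference. Nothing says that order is kept between sessions, and it is unclear whether a baseline task is run at all.

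A reader might infer that omitting order confounds the treatment effect, or that a wider interval and chance imbalance are two separate harms. The documents support neither. Treatment is randomised, so the estimate is unbiased and the type I error holds, and the imbalance is the same variance seen another way (step 3 of the working).

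**Conclusion.** The point holds as a modest loss of precision. A randomised design factor is missing from the stated Hypothesis 3a model, and balance of order within arm is not stated. The size depends wholly on an order effect that the documents do not give. Comparing simulated power with and without the term, the gain is nil at 0.3 residual SD, about 1 point at 0.5, and about 8 points at 1.0. With no order effect at all, the term costs just under 1 point. Nothing in the documents shows that an effect as large as 1.0 is likely.

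These figures assume 48 analysed participants, a 24/24 split of order, order drawn without regard to arm, and an order effect that does not cancel in the change from baseline.

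A more basic problem lies in the same section. Section 20.3.3 calculates the score at baseline and week 6 (T8) but places the contrasts at T6. Sections 4.2.2 and 7.1.8 and the T6 visit schedule give the task at week 4. Section 4.1 gives it at baseline and the end of six weeks. The baseline visit in section 7.3.2 lists only the collection of scripts. Without a baseline task, neither the trial-time term nor the change contrast can be estimated.

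**What to change.** - In the formal SAP, pre-specify a fixed factor for trauma before v after neutral in the Hypothesis 3a models for craving, negative emotion and psychophysiological arousal.
- For participants not yet tested, balance imagery order within arm through the coded randomisation list, so that staff running the task stay blinded. With six orders, 30/6 = 5 and 18/6 = 3, so exact balance is possible at the planned numbers.
- Record the order actually run, and state whether it is kept or redrawn if the task is given more than once.
- Define Pre and Post, and reconcile the task timing across sections 4.1, 4.2.2, 7.1.8, 7.3 and 20.3.3.

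The cost is one degree of freedom and no new data beyond the order run, with no gain if the order effect is small. The effect detectable with 0.80 power moves from 0.853 to 0.854, before the loss of about 1 power point from chance non-orthogonality that within-arm balance would avoid.

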### 20.3.2 Analysis of the Primary Endpoint(s)

For Hypothesis 1a, Safety and tolerability, the frequency of adverse events will be analyzed for the entire sample at all time points, tabulated for each treatment group, and compared using chi-squared tests. The safety analysis will be largely descriptive of outcomes for the entire study population. The incidence of AEs will be summarized by system organ class, preferred term, the likelihood of its relationship to the treatment, and severity for each treatment group. Clinical laboratory data will be summarized by type of test. Frequency and percentage of patients whose values fall outside of reference ranges will be presented for each measurement.

For Hypothesis 1b, Alcohol Use. The Primary outcome measure, number of drinks per day, will be analyzed with an MMRM to assess differences in change from baseline. The primary contrast is change from baseline (B1) at week 6 (T8). The model at each time point will include terms for treatment, time and treatment by time interaction as factors and the baseline value for each score as a covariate. Parameter estimation will be based on REML and to begin an unstructured covariate matrix will be used. If the model fails to converge, the form of the covariance matrix will be chosen based on Akaike's Information Criteria, and Schwarz' Bayesian Criterion. Model-based LS means will be obtained for change from baseline to each time point for each treatment group. At each time point, contrasts between CBD and placebo will be obtained. Secondary alcohol use measures will be tested with MMRM sequentially in a closed testing union intersection paradigm in the order listed in section C.8.3. Validity of the p-value will extend until the first test fails to have a p-value smaller than a two-sided alpha of 0.05. The analyses will continue for all measures but the resulting p-value will be nominal.

For Hypothesis 2, PTSD symptoms, the primary outcome measure, total score of the PCL-5, will be analyzed in the same way as the primary outcome for alcohol use. The primary contrast is change from baseline (B1) at week 6 (T8).

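### Trauma-craving task (Hypothesis 3a): a baseline contrast with no margin is read as group equivalence, and the listed model has no baseline covariate, in conflict with the Protocol Summary

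*Combined protocol and SAP*

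**What the plan says.** Section 20.3.3 (Hypothesis 3a) defines the craving outcome as a difference of difference scores: trauma against neutral, post against pre. On timing it says: "This difference measure of alcohol craving will be calculated at Baseline, and at week 6 of the clinical trial (T8"). The model has "fixed effects for treatment C, (CBD vs. placebo) and clinical trial time T, a random effect for subjects"; the only other term listed is the interaction of the first two. One planned contrast is described in these words: "Between treatment outcome contrasts will be performed at Baseline, as a measure of the equivalence of the groups". Two more comparisons of the arms are planned, one on the T6 scores and one on the change from Baseline to T6. The link back to the primary analysis concerns only the covariance structure: "the form of the covariance matrix will follow the procedures described for the analysis of Aim 1". Negative emotion and psychophysiological arousal are analysed similarly.

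For drinks per day, section 20.3.2 has "the baseline value for each score as a covariate", and PCL-5 follows it. The Statistical Analysis part of the Protocol Summary says that the traumatic-stress craving outcome from the laboratory task is also analysed in the manner of drinks per day.

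Section 20.3.1 sets two-sided tests, with 0.05 significant and 0.10 suggestive, and makes effect sizes the main focus.

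The documents disagree on when the task is done. Sections 2.3 and 4.1 have it at baseline and at the end of treatment. The task description in 4.2.2, section 7.1.8 and the visit lists in 7.3 place it at T6 (4 weeks) only, with imagery scripts alone collected at baseline.

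**The concern.** Three things are at issue.

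- **Equivalence.** The absence of a detected difference is not evidence of equivalence, least of all with 18 in the smaller arm. In a randomised trial a baseline difference is a chance event, so a between-arm contrast on it answers no useful question.
- **Baseline as response only.** With treatment, time and their interaction fitted to baseline and follow-up, and complete data, the fitted on-treatment contrast is the raw difference in follow-up means, and the change contrast is the raw difference in mean change. Neither uses the correlation between sessions as a baseline covariate would.
- **Two contrasts and no hierarchy.** When the arms differ at baseline by chance, the two contrasts move in opposite directions. The plan does not say which one is the result.

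The background section presents this kind of task as a possible measure of target engagement. An imprecise or ambiguous effect estimate would therefore weaken the use of the pilot for planning.

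**Working it through.** **Inputs.** Arm sizes are 30 and 18 (section 20.5.1). Tests are two-sided at 0.05, with 0.10 suggestive (20.3.1). The correlation rho between the baseline and follow-up task scores is not in the documents; it is assumed, with equal SDs at both sessions. The differences of 0.3, 0.5 and 0.8 SD are also illustrative assumptions.

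**The plan's own power figure.** Section 20.4 gives an effect size of 0.939 for 0.8 power by t test. At 30 v 18 the exact noncentral t calculation (46 df) needs 0.853, and 0.939 gives power 0.869. The stated figure reproduces at 25 v 15, a size the plan does not state. No power figure is given for the baseline contrast.

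**What the baseline contrast can show.**
- SE of a standardised difference = sqrt(1/30 + 1/18) = 0.298.
- The critical t on 46 df is about 2.013, so the observed difference must exceed 2.013 × 0.298 = 0.60 SD for p ≤ 0.05. An observed 0.5 SD gives p = 0.10.
- For a true difference of 0.5 SD, power is 0.375, so 1 − 0.375 = 0.625 goes undetected. At 0.3 SD it is 83%.
- At the suggestive 0.10 level the figure for 0.5 SD is still 50%.
- Randomisation alone produces an observed imbalance of at least 0.5 SD, in either direction, about 9% of the time.

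**Effect of a chance imbalance D (in SDs).** The expected shift is +rho × D in the on-treatment contrast and −(1 − rho) × D in the change contrast. For D = 0.5:

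| rho | On-treatment | Change |
|---|---|---|
| 0.3 | +0.15 | −0.35 |
| 0.5 | +0.25 | −0.25 |
| 0.7 | +0.35 | −0.15 |

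**Precision and power.** Relative variances are 1 (on-treatment), 2(1 − rho) (change) and 1 − rho² (baseline as covariate). At rho 0.3 these are 1, 1.40 and 0.91; at rho 0.5 they are 1, 1 and 0.75. Power for a 0.8 SD effect:

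| rho | Change | On-treatment | Adjusted |
|---|---|---|---|
| 0.3 | 60% | 75% | 78% |
| 0.5 | 75% | 75% | 85% |

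For example, the change contrast at rho 0.3 has an effective size of 0.8/sqrt(1.40) = 0.676, for which the exact t test has power 0.60.

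**Type I error.** Simulation of null trials at 30 v 18 gives about 5% for both planned contrasts over all randomisations. Excess appears only within a selected subset. About 13% of trials have a non-significant baseline contrast together with an imbalance of at least 0.4 SD. In these, at rho 0.3, the rates are about 6% (on-treatment), 10% (change) and 5% (adjusted).

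**The case against.** Several stronger readings are tempting, and the documents do not support them.

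- **That a p-value decides equivalence.** Section 20.3.3 gives no test threshold, no pass or fail and no consequence. The 62% holds only if the general 0.05 rule is carried over and 0.5 SD is taken as the difference of interest. This stands as a limit on the figure. It does not rescue the wording, since the plan then offers no criterion for equivalence at all.
- **That the analysis ignores baseline.** It does not. Baseline is in the response vector and the change contrast subtracts it. What is absent from 20.3.3 is the covariate, and the Protocol Summary can fairly be read as supplying it. Section 20.3.1 also refers to fully adjusted models. The documents therefore hold two descriptions that need reconciling.
- **That the planned tests are biased or inflate type I error.** Over randomisation both are unbiased with about 5% error. The bias is conditional on an imbalance that has occurred.
- **That much power is lost whichever contrast is used.** At rho 0.3 the on-treatment contrast loses only 3 points against the adjusted one (75% v 78%). The large loss at that correlation belongs to the change contrast.

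It is also fair to say that this is a secondary outcome in a small pilot, and that section 20.1 leaves a formal SAP still to be written. That limits the severity and makes the correction easy.

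**Conclusion.** The point holds in a limited form. The equivalence reading should go: at 30 v 18 an imbalance of up to about 0.60 SD would pass unflagged under the 0.05 rule. Section 20.3.3 lists no baseline covariate, in conflict with the Protocol Summary read together with 20.3.2, and it leaves two contrasts with opposite conditional shifts and no order between them. The consequence is lost precision and an ambiguous effect estimate; the planned tests remain valid.

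The gain from adjustment is 3 to 18 percentage points of power for 0.8 SD at rho 0.3 and 10 points at rho 0.5, depending on the contrast replaced. It rests on the assumed rho, equal SDs and all 48 analysed.

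All of this presupposes a baseline task session. If the task is run at T6 only, neither the baseline contrast nor the change contrast can be computed, and there is no baseline score to adjust for.

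**What to change.** 1. Reconcile the schedule first. State whether a baseline task session is run (sections 2.3, 4.1 and 20.3.3 against the task description in 4.2.2, section 7.1.8 and the visit lists in 7.3), and whether the post-baseline time is T6 or T8, since 20.3.3 names both.
2. If the baseline session is run, delete the equivalence contrast from 20.3.3 and report baseline means and SDs by arm. Name one primary contrast: the on-treatment difference between arms with the baseline task score as covariate, or equally a repeated-measures model with a common baseline mean. This agrees with the Protocol Summary and 20.3.2. Apply the same to negative emotion and psychophysiological arousal.
3. If the baseline session is not run, delete the baseline and change contrasts and align the Hypothesis 3a wording in 20.2, which speaks of a reduction from baseline.

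The cost is wording in the protocol and the formal SAP, and one degree of freedom for the covariate.
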